1855 **Stopping Rules for Subjects during the outpatient portions of the study (that will not**
1856 **result in stopping of the entire study):**

- 1857
- Medical need for repeated doses of Tylenol / acetaminophen
 - 1858 • Medical need for oral or injected glucocorticoids
 - 1859 • Positive pregnancy test
 - 1860 • At Visit 2 review of the blinded CGM shows that the CGM was functional
 - 1861 $\leq 80\%$ of the time or LBGI ≤ 1.1
 - 1862 • If after completion of 1 week of the AP system Pump mode home use, the
 - 1863 investigator determines that the subject cannot be adequately monitored at least
 - 1864 75% of the time in their local environment.
 - 1865 • If after the Visit 4 Study Pump and the AP system Training, the subject is
 - 1866 unable to complete system-related tasks independently.
 - 1867 • If during Home Use with the AP system in Pump Mode the subject failed to use
 - 1868 the system for more than 80% of the time during this phase or the subject could
 - 1869 not be adequately monitored at least 75% of the time in their local environment
 - 1870 by the final day of home use.
 - 1871 • If after the Visit 5 USS Virginia Training, the subject is unable to complete
 - 1872 system-related tasks independently.
 - 1873 • If during a second Closed Loop Mode Home Use Trial Period the subject used
 - 1874 the system in the appropriate mode $< 80\%$ of the time during the day and night
 - 1875 or the remote monitoring was functional $< 75\%$ of the time.
 - 1876 • If study staff are persistently unable to contact the subject or the care partner in
 - 1877 a timely manner during the course of the study.
- 1878

1879 **Study Procedures will be put on hold during the outpatient portions of the study if:**

- 1880
- Fingerstick β -hydroxybutyrate level ≥ 3.0 mmol/L
 - 1881 • Abdominal pain
 - 1882 • Vomiting illness
 - 1883 • Unable to eat or drink

- 1884 • Fever ≥ 101.5 °F
- 1885 • Clinical need for Tylenol / acetaminophen
- 1886 • Significant illness
- 1887 • Use of epinephrine to treat a severe allergic reaction or asthma

1888

1889 **Stopping Rules for the Entire study:**

1890 The study will be stopped if three similar AE’s occur that result in individual subjects
 1891 stopping the study (except those identified above that will not stop the entire study) or if
 1892 there are system communication failures, which may trigger revision of the system
 1893 software. Additionally, the Principal Investigator, IRB-HSR, the Data Safety Monitoring
 1894 Board (DSMB), or sponsor may decide to stop the trial or part of the trial at any time. In
 1895 this case, the Principal Investigator will promptly inform the subjects and assure
 1896 appropriate therapy and follow-up. Additionally the Principal Investigator will notify the
 1897 IRB and DSMB if the study is temporarily stopped. The pertinent regulatory authorities
 1898 will be informed according to national regulations. The DSMB will meet to determine if
 1899 changes to the protocol or system are needed prior to restarting the study and whether the
 1900 study may be restarted.

1901

1902 Early study stop will be documented and following information will be collected:

- 1903 > Date and cause of the ending
- 1904 > Description of any serious adverse event leading to the study ending

1905

1906 A subject who does not complete the at least 1 week of the study intervention may
 1907 be replaced. Available data will be exploited.

1908

1909 In the case of an unanticipated adverse device effects (UADE), the overall study may be
 1910 suspended while the problem is diagnosed and the PI investigates the UADE. If the PI
 1911 determines that the UADE poses an unreasonable risk to subjects, the study should be
 1912 suspended until this UADE can be resolved. If it cannot be resolved, the study should be
 1913 terminated. Termination should occur no later than 5 working days after PI makes the
 1914 decision. The result of the investigation and the PI’s decision to terminate the study shall
 1915 be reported the site IRB, and the FDA per 21CFR 812.46(b) (2). The DSMB must
 1916 determine if the UADE presents an unreasonable risk to subjects. If so, the DSMB must
 1917 ensure that all investigations, or parts of investigations presenting that risk, are terminated
 1918 as soon as possible but no later than 5 working days after the DSMB makes this
 1919 determination and no later than 15 working days after first receipt notice of the UADE.

1920

1921 The study may resume if the underlying problem can be corrected by a protocol or
 1922 system modification that will not invalidate the results obtained prior to suspension. The
 1923 IRB and DSMB will be notified if the study is stopped, and permission to resume will be
 1924 obtained from the FDA, DSMB and IRB prior to restarting.

1925

1926 **CATASTROPHIC EVENT PLAN**

1927 The Outpatient Emergency Plan will go into effect should a catastrophic event occur
 1928 during any monitored outpatient setting (Visit 4 or Visit 5). A catastrophic event is
 1929 defined as any event that requires emergency treatment by medical professionals that
 1930 exceed the expected parameters of the protocol. A copy of this plan will be located at the
 1931 monitoring desk. Staff will be aware of its location at all times.
 1932

Event	RN Response	Tech Response
Respiratory Arrest	1) Tell Tech to call 911 2) Begin Basic Life Support	Refer to Study Physician
Cardiac Arrest	1) Tell Tech to call 911 2) Begin Basic Life Support	Refer to Study Physician
Severe Hypoglycemic Event as defined by hypoglycemia accompanied by unconsciousness or seizure	1) Tell Tech to call 911 2) Administer glucagon IM (described in Outpatient Hypoglycemia, Hyperglycemia and Ketone Treatment Instructions APPENDIX A-12) 3) Remove study pump	Refer to Study Physician
Severe Hyperglycemic Event as defined by β -ketone level ≥ 3.0 mmol/L	1) Discuss correction dose of insulin to administer s.c. via syringe with study M.D. 2) Encourage p.o. water intake 3) Remove study pump and start home insulin pump 4) Go to nearest medical facility for evaluation and treatment.	Refer to Study Physician

1933 **Table 2: Outpatient Emergency Plan**

1934 In the unlikely event of a disruption in 911 phone service, the sites will contact their local
 1935 non-emergency number (e.g. Charlottesville-UVA-Albemarle Emergency
 1936 Communications Center can be reached via their non-emergency number [contact]).
 1937 This number feeds into their main call area where 911 dispatchers are available 24/7.
 1938

1939 **DATA AND SAFETY MONITORING PLAN**

1940 **Adverse Events, Unanticipated Problems, Protocol Violations and Data Breaches**
 1941 **Reporting Table**

Type of Event	To whom will it be reported:	Time Frame for Reporting	How reported?

Any internal event resulting in death that is deemed DEFINITELY related to (caused by) study participation (Note: An internal event is one that occurs in a subject enrolled in a UVa protocol.)
	
IRB-HSR, DSMB
	
Within 24 hours
	
IRB Online and phone call www.irb.virginia.edu/

Internal, Serious, Unexpected adverse event.
	
IRB-HSR, DSMB
	
Within 7 calendar days from the time the study team received knowledge of the event. Timeline includes submission of signed hardcopy of AE form.
	
IRB Online www.irb.virginia.edu/


For Device Studies: Unanticipated adverse device effects (internal)
	
IRB-HSR, DSMB
	
Within 10 day calendar days of the study team receiving knowledge of the event
	
IRB Online www.irb.virginia.edu/

Unanticipated Problems that are not adverse events or protocol violations This would include a Data Breach.
	
IRB-HSR
	
Within 7 calendar days from the time the study team received knowledge of the event.
	
Unanticipated Problem report form. http://www.virginia.edu/vprgs/irb/HSR_docs/Forms/Reporting_Requirements-Unanticipated_Problems.doc)

Protocol Violations The IRB-HSR only requires that MAJOR violation be reported, unless otherwise required by the sponsor
	
IRB-HSR
	
Within 7 calendar days from the time the study team received knowledge of the event.
	
Protocol Violation and Enrollment Exception Reporting Form http://www.virginia.edu/vprgs/irb/hsr_forms.html Go to 3rd bullet from the bottom

Data Breach	
The UVa Corporate Compliance and Privacy Office, a
 
ITC: if breach involves electronic data-
 
UVa Police if breach includes such things as stolen computers.
	
As soon as possible and no later than 24 hours from the time the incident is identified.
 
As soon as possible and no later than 24 hours from the time the incident is identified.
 
IMMEDIATELY.
	
UVa Corporate Compliance and Privacy Office- [contact]
 
ITC: Information Security Incident Reporting procedure, http://www.itc.virginia.edu/security/reporting.html
 
Phone- [contact]

UVA PI- IDE			
Life-threatening and/or fatal unexpected events related or possibly related to the use of the investigational agent.	FDA, DSMB	Within 7 calendar days of the study team learning of the event	Form FDA 3500A (MedWatch) or narrative
Serious, unexpected and related or possibly related adverse events	FDA, DSMB	Within 15 calendar days after the study team receives knowledge of the event	Form FDA 3500A (MedWatch) or narrative
For Device Studies: Unanticipated adverse device effects (internal or external)	FDA, DSMB	Within 10 working days of the study team receiving knowledge of the event	Form FDA 3500A (MedWatch) or narrative
All adverse events	FDA, DSMB	Annually	IDE annual report
UVA PI of MULTI-SITE TRIAL			
Serious, unexpected and related or possibly related adverse events	All Research Sites	Within 15 days after the Overall PI receives knowledge	IND/IDE Safety Report (Cover letter, copy of MedWatch/narrative)

		of the event.	
For Device Studies: Unanticipated adverse device effects (internal or external)	All Research Sites	Within 15 calendar days from the time the Overall PI receives knowledge of the event.	Letter to Participating PIs, Copy of MedWatch or narrative
Unanticipated Problem	All Research Sites	Within 15 calendar days from the time the Overall PI receives knowledge of the event.	Letter to Participating PIs, Copy of MedWatch or narrative

1942
1943

1944

J. ENDPOINTS

1945
1946
1947
1948
1949
1950
1951
1952
1953
1954
1955
1956

This study is a randomized, controlled trial involving subjects with type 1 diabetes to test the effectiveness of the Unified Safety System (USS) Virginia closed-loop in preventing hypoglycemia compared with sensor-augmented pump (SAP) therapy. We will also evaluate the effectiveness of the control system (USS Virginia) at improving hypoglycemia counterregulation, hypoglycemia awareness, and overall glycemic control compared with versus SAP. To achieve this goal, we will conduct pre- and post-intervention inpatient assessments of hypoglycemia counterregulation and symptom awareness. For the interventions, subjects randomized to USS Virginia will participate in two training visits at a monitored outpatient setting for the step-wise deployment of the AP system at home in Pump mode followed by 4 weeks using AP at home in Closed Loop mode running USS Virginia. Subjects randomized to sensor-augmented pump therapy will complete 5 weeks of CGM with the home pump.

1957
1958
1959
1960
1961
1962

The basic unit for analyses of hypoglycemia risk and occurrence is the glucose trace of an individual, i.e. a time-stamped series of CGM data recorded for each person. Summary characteristics and group-level analyses are derived after the individual traces are processed to produce meaningful individual markers of average glycemia and glucose variation.

1963
1964
1965

The following primary endpoint of reduction in hypoglycemia will be assessed by:
1. LBGI from CGM during 1 week of blinded use versus during the last week of

1966 intervention

1967

1968 The secondary endpoints of improvement in counterregulatory response to hypoglycemia and
 1969 hypoglycemia awareness at baseline versus follow-up will be assessed by:

- 1970 1. Peak epinephrine
- 1971 2. Epinephrine AUC
- 1972 3. Epinephrine increase over baseline
- 1973 4. Hypoglycemia symptom ratings
- 1974 5. Clarke Hypoglycemia Perception Awareness score
- 1975 6. Fear of hypoglycemia scores

1976

1977 Additional secondary endpoints of reduction in hypoglycemia will be assessed by:

- 1978 1. CGM time <70 mg/dL and <50 mg/dL by retrofitted CGM and SMBG trace from 1
 1979 week of blinded use versus the last week of intervention
 - 1980 a. During 24 hours, and
 - 1981 b. Overnight (11PM – 7AM)

1982

1983 Additional secondary endpoints of improvement in glycemic control at baseline versus the
 1984 last week of intervention will be assessed by:

- 1985 1. Time within target (70-180 mg/dL) over a 24 hour period
- 1986 2. Time within target range of 80-140 mg/dL overnight (11PM – 7AM), and
- 1987 3. Distribution of wake-up glucose levels at 7AM

1988

1989 **K. SUCCESS CRITERIA / GOAL**

1990 As a general rule, a subject’s data will be considered useful for data analysis if the
 1991 subject completes at least 1 week of study intervention with USS Virginia+AP system or
 1992 SAP.

1993 **L. STATISTICAL ANALYSIS PLAN**

1994 Sample size determination is based on literature data (#3) and on results from our
 1995 previous studies of hypoglycemia unawareness (#4)(#5). We estimate, conservatively,
 1996 that the effect size of using the AP system+USS Virginia vs. CGM in terms of
 1997 restoration of epinephrine response will be moderate ~0.35. Power calculations assuming
 1998 $\alpha=0.05$, and power of 80% yield a required sample size of N=36 (using G*Power 3
 1999 software [#5]). With this sample size, the power for finding significant effects on
 2000 frequency and extent of hypoglycemia (Low BG Index [#6]) exceeds 0.9. Assuming a
 2001 proportion of noncompliance R=20% for Intention-to-Treat (ITT) analysis (#7), 44
 2002 completed subjects will adequately address the specific aims of this study. Per-protocol
 2003 analysis will also be performed. In order to achieve 44 completed subjects, up to 70

2004 subjects may sign consent given an expected screen failure, withdrawal and drop-out rate
2005 of ~40% due to the rigorous exclusion criteria and requirements imposed for the AP
2006 system use in the subject's local environment.
2007
2008

2009 REFERENCES

- 2010 #1 Diabetes Research in Children Network (DirecNet) Study Group, Tsalikian E,
2011 Tamborlane W, Xing D, Becker DM, Mauras N, Fiallo-Scharer R, Buckingham B,

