48 versus sensor-augmented pump (SAP) therapy for hypoglycemia prevention in subjects with
49 type 1 diabetes and hypoglycemia unawareness and/or risk for hypoglycemia.

[figure not shown]
50 Subjects: We will recruit up to 85 subjects aged 12-70 years old with type 1 diabetes
51 for at least the past 1 year, on insulin for at least the past 1 year, and on insulin pump
52 therapy for at least the past 6 months to achieve a goal of 44 completed subjects.

53 Subjects will be recruited at two clinical sites: University of Virginia and Stanford
54 University.

55 Procedure: Figure 1 below presents the overall flow of the study.

56

Figure 1: Study flow diagram

Visit 1: Screening 1 Visit. A meter ± CGM download will be performed to evaluate subject

60 eligibility (i.e. Average Daily Risk Range [ADRR] >40 or LBGI >2.5 from SMBG data or
61 LBGI >1.1 from 1 week of CGM data within the prior 3 weeks) and to determine pre-study
62 CGM use in the prior 4 weeks (active [CGM use \geq 5 days/week] or no CGM use). Baseline
63 HbA1c, hypoglycemia symptom awareness (presence of adrenergic symptoms at BG 60
64 mg/dL) and hypoglycemia questionnaires (Clarke Hypoglycemia Perception Awareness and
65 Fear of Hypoglycemia – APPENDIX A-5) will be assessed. Those subjects that qualify will
66 be trained to use the study glucometer and CGM in blinded mode and complete 1 week of
67 baseline blinded CGM and SMBG at least 4 times daily.

68

69 **Visit 2: Screening 2 Visit.** The blinded CGM will be downloaded and if review of the data
70 shows that the CGM was functional >80% of the time and the subject has confirmed risk of
71 hypoglycemia with LBGI >1.1 (#2) (per 1 week of blinded CGM), the subject will be
72 randomized to USS Virginia AP system experimental treatment or Sensor-Augmented Pump
73 Therapy control treatment and proceed to Visit 3. The experimental and control groups will
74 be matched for LBGI and pre-study CGM use. The study glucometer will be downloaded
75 and assessed for average SMBG/day and randomness of data. Subjects with average SMBG
76 <3.5/day and/or poor randomness of SMBG testing will be reminded of SMBG requirements
77 4-6 times daily (pre-meal, bedtime, before driving, before exercise, and as indicated). CGM
78 data collection period may be repeated.

79

80 **Visit 3: 8 hr Inpatient Assessment of Hypoglycemia Counterregulation and Symptom**
81 **Awareness.** The subjects will undergo hypoglycemia induction via a previously validated

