172 counted in the enrollment tally.

173 **D. Sample Size and Investigational Sites**

174 The studies will be conducted at University of Virginia and Stanford and will require IRB
175 approval at each site prior to the initiation of the trial.

176

177 At the University of Virginia, all inpatient studies (Visit 3 and Visit 6) will be performed at
178 the Clinical Research Unit (CRU) of the University of Virginia Health System with website

179 at: ([http://research.med.virginia.edu/clinicalresearch/research-resources/offices-supporting-](http://research.med.virginia.edu/clinicalresearch/research-resources/offices-supporting-clinical-research/clinical-research-unit/)
180 [clinical-research/clinical-research-unit/](http://research.med.virginia.edu/clinicalresearch/research-resources/offices-supporting-clinical-research/clinical-research-unit/)). The street address is:
181 UVA Medical Center
182 [name]
183 [name]

184
185 The monitored outpatient studies (Visit 4 and Visit 5) will occur at a UVa CRU.

186
187 At Stanford, all inpatient studies (Visit 3 and Visit 6) will be performed at The Stanford
188 Center for Clinical and Translational Research and Education (CTRU) with website at:
189 <http://spectrum.stanford.edu/accordions/clinical-and-translational-research-unit>.

190
191 The monitored outpatient studies (Visit 4 and Visit 5) will in 3 rooms available for
192 outpatient research studies through “ACCESS”, a clinical research resource available at
193 Stanford. These rooms are available in the same building as the Endocrine Division and are
194 adjacent to the CTRU.

195
196 Forty-four subjects (N=44) with type 1 diabetes mellitus will be needed to complete the
197 protocol.

198
199 Based on our experience with similar studies and the additional requirement of
200 hypoglycemia unawareness or risk for hypoglycemia, we estimate an expected ~40% screen
201 failures, dropouts, or withdrawals, thus we intend to set a recruiting target of 70 subjects.

202 203 **Hypothesis:**

204 We hypothesize that in patients with hypoglycemia unawareness and a risk for
205 hypoglycemia, the AP system equipped with USS Virginia compared with CGM-augmented
206 pump therapy will result in:

- 207 1. Reduced risk for hypoglycemia and exposure to hypoglycemia (measured by the
208 Low Blood Glucose Index and by CGM time in hypoglycemia).
- 209 2. Restoration of hypoglycemia counterregulation (as assessed by epinephrine

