210 response measured in a hospital setting), restoration of hypoglycemia awareness,
211 and reduced fear of hypoglycemia.

212 213 **Primary Specific Aim:**

214 Reduction in hypoglycemia during the study on USS Virginia versus SAP as assessed by:

- 215 • LBGI from CGM during 1 week of baseline blinded use versus during the last week
216 of intervention.

217 218 **Secondary Specific Aims:**

219 Reduction in hypoglycemia during the study on USS Virginia versus SAP as assessed by:

- 220 • CGM time <70 mg/dL and <50 mg/dL by retrofitted CGM and SMBG trace during a
 221 24 hour period and the overnight period (11PM – 7AM) from 1 week of baseline
 222 blinded use versus the last week of intervention.
 223

224 Improvement in counterregulatory response to hypoglycemia at baseline versus follow-up as
 225 assessed by:

- 226 • Peak epinephrine
 227 • Epinephrine area under the curve (AUC)
 228 • Epinephrine increase over baseline
 229

230 Improvement in hypoglycemia awareness at baseline versus follow-up as assessed by:

- 231 • Hypoglycemia symptom ratings
 232 • Clarke Hypoglycemia Perception Awareness and Fear of Hypoglycemia scores
 233

234 Improvement in glycemic control at baseline versus the last week of intervention as assessed
 235 by:

- 236 • Time within target (70-180 mg/dL) over a 24 hour period.
 237 • Time within target (80-140 mg/dL) in the overnight period (11PM – 7AM)
 238 • Distribution of wake-up glucose levels at 7AM
 239

240 Sample size determination is based on literature data (#3) and on results from our previous
 241 studies of hypoglycemia unawareness (#4)**Error! Reference source not found..** We
 242 estimate, conservatively, that the effect size of using the AP system+USS Virginia vs. CGM
 243 in terms of restoration of epinephrine response will be moderate ~0.35. Power calculations
 244 assuming $\alpha=0.05$, and power of 80% yield a required sample size of N=36 (using G*Power
 245 3 software [#5]). With this sample size, the power for finding significant effects on
 246 frequency and extent of hypoglycemia (Low BG Index [#6]) exceeds 0.9. Assuming a
 247 proportion of noncompliance R=20% for Intention-to-Treat (ITT) analysis (#7), 44
 248 completed subjects will adequately address the specific aims of this study. Per-protocol
 249 analysis will also be performed. In order to achieve 44 completed subjects, up to 70 subjects
 250 may sign consent given an expected screen failure, withdrawal and drop-out rate of ~40%

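### The maximum number of subjects is 85 in Section B but 70 in Sections D and L, for the same goal of 44 completers, and the two limits are not reconciled

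*Combined protocol and SAP*

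**What the plan says.** Section B (Study Design Overview), on subjects: "Subjects: We will recruit up to 85 subjects aged 12-70 years old with type 1 diabetes". The sentence ends with its purpose: "therapy for at least the past 6 months to achieve a goal of 44 completed subjects". It attaches no loss rate to the 85.

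Section D (Sample Size and Investigational Sites) gives the same requirement: "Forty-four subjects (N=44) with type 1 diabetes mellitus will be needed to complete the" protocol. It then gives the expected loss, "hypoglycemia unawareness or risk for hypoglycemia, we estimate an expected ~40% screen" failures, dropouts or withdrawals combined, and draws the consequence: "failures, dropouts, or withdrawals, thus we intend to set a recruiting target of 70 subjects".

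The sample size paragraph at the end of Section D turns 70 into an upper limit on consent, again for 44 completers and again at about 40% loss: "analysis will also be performed. In order to achieve 44 completed subjects, up to 70 subjects" may sign consent. Section L (Statistical Analysis Plan) repeats this: "In order to achieve 44 completed subjects, up to 70" subjects may sign consent, with the same approximate loss.

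**The concern.** A maximum sample size is an operational limit, so it needs a single value. Here Section B permits 85, while the sample size section and the SAP permit 70. All three serve the same completer goal, and the trial needs IRB approval at each of its two sites.

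If recruitment follows Sections D and L, consent closes at 70. At exactly the stated loss, the expected yield is then slightly under the target. If recruitment follows Section B, up to 15 further people may be consented beyond the limit in the section that justifies the sample size. The same conduct would be compliant under one section and a deviation under another, and a monitor or ethics board could not tell which from the document.

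**Working it through.** **Inputs**
- Completers required: 44 (Sections B, D and L).
- Loss from consent to completion, including screen failures: about 40% (Sections D and L).
- Maximum: 85 (Section B); 70 (end of Section D, and Section L).
- Recruiting target: 70 (Section D).

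**Size of the contradiction.** 85 − 70 = 15 subjects, and 15/70 = 21% of the lower limit.

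**Could the two numbers measure different things?**
- Pilot subjects: Section C leaves them out of the enrollment tally, so they do not account for the 15.
- Recruited versus consented: Section B speaks of recruiting, and the end of Section D speaks of signing consent. But Section D also calls 70 the recruiting target, and its loss includes screen failures. Both terms therefore cover intake before screening losses.
- Replacements: Section I lets a subject with less than one week of intervention be replaced, but gives no number and no link to 85. Withdrawals are already inside the 40%.

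**Reproducing the plan's 70.** Consents needed = completers / (1 − loss) = 44 / (1 − 0.40) = 44 / 0.60 = 73.3, so 74. The incorrect inflation 44 × 1.40 = 61.6, so 62, does not give 70 either. The loss at which 70 yields exactly 44 is 1 − 44/70 = 37.1%.

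**Expected completers = maximum × (1 − loss)**

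| Loss | From 70 | From 85 |
|---|---|---|
| 35% | 45.5 | 55.3 |
| 37.1% | 44.0 | 53.5 |
| 40% | 42.0 | 51.0 |
| 45% | 38.5 | 46.8 |

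**Chance of at least 44 completers.** This assumes that each consented subject completes independently with the same probability; the plan does not state that assumption.

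| Loss | 70 consents | 74 consents | 85 consents |
|---|---|---|---|
| 35% | 0.70 | 0.87 | above 0.99 |
| 40% | 0.36 | 0.59 | 0.95 |
| 45% | 0.11 | 0.26 | 0.76 |

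At 40% loss, 74 makes the expected number just over 44 (74 × 0.60 = 44.4) but reaches 44 only a little more often than not. A maximum of 85 works as a ceiling with margin.

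**The case against.** Four arguments can be made against the point.

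1. **A target of 70 can sit beside a maximum of 85.** This is right for the recruiting-target sentence in Section D taken alone. It does not cover the end of Section D and Section L, where 70 is itself worded as an upper limit on consent. The conflict is between those two places and Section B.

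2. **The shortfall of 42 against 44 is rounding.** This largely stands. The loss is written as approximate, 37% could fairly be described as about 40%, and at that rate 70 gives 44. The gap of 2 is a note on consistency and would not carry the point alone.

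3. **Power is not lost.** This also stands in the main. The stated calculation requires 36, and 44 adds an allowance for 20% noncompliance. Under that allowance 42 leaves 42 × 0.80 = 33.6 compliant subjects, against 44 × 0.80 = 35.2. Section K also treats data as usable after one week of intervention, so usable subjects may outnumber completers. A reader might infer that the trial would be underpowered at 70; the documents do not support that on this ground.

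4. **85 does not imply a different loss rate.** A reader might back-solve 1 − 44/85 = 48.2% and infer that Section B assumes 48% loss. It does not: Section B gives a maximum with no rate attached, and 85 is compatible with about 40% loss as a ceiling with margin. It is equally tempting to assume that 85 is the current figure and 70 a leftover, but nothing in the document shows which is current.

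**Conclusion.** The contradiction stands and should be fixed: for the same 44 completers, the maximum is 85 in Section B and 70 in Sections D and L, a difference of 15 subjects. No other provision in the document accounts for it. The consequence is an undefined enrollment limit for subjects 71 to 85 across the two sites.

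The arithmetic point is secondary. At exactly 40% loss, 70 consents give an expected 42 completers, 2 short, and 74 would be needed. The size of that gap depends on reading an approximate rate as exact. The probabilities rest in addition on independent completion at a common rate.

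The point does not touch the N=36 calculation, the 44-completer requirement, any endpoint or any analysis.

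**What to change.** The sponsor should confirm which maximum was approved, then:

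- State that one number in Sections B, D and L, labelled as a study-wide ceiling on subjects who sign consent.
- If a lower recruiting target is also wanted, give it separately and label it as a target.
- Make the number agree with the stated loss. At 40%, at least 74 consents are needed for an expected 44 completers; 85 can be kept with about 40% loss if it is described as a ceiling with margin. If 70 is kept as the ceiling, restate the assumed loss as about 37%.
- Do not restate the expected loss as 48%. That rate is only back-calculated from 85, and nothing in the document supports it.

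The cost is wording in three sections if the confirmed number is the one already approved. A maximum above the approved one would need IRB approval at both sites. No endpoint, randomization or analysis changes.
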